### 4. REGISTRATION PROCEDURES

Once informed consent is signed:

- Attach scanned copy of completed eligibility checklist in OnCore for review by the CRSO/designated safety monitor at the time of quarterly audits.
- Enter subject into the OnCore database of the Holden Comprehensive Cancer Center.
- Scan the record of consent into the subject's medical record.

### 5. PROCEDURES

Protocol should not supersede standard of care procedures for patient safety.

#### 5.1. Imaging preparation

- 5.1.1. **Oral hydration.** Participants will be encouraged to maximize hydration the day before and day of  $^{68}\text{Ga}$  PSMA-HBED-CC imaging.
- 5.1.2. **Furosemide.** 20 mg furosemide (IV push) will be administered concurrently or immediately after radiotracer administration to minimize PET scatter artifacts from excreted radiotracer accumulation in the kidney and urinary

bladder.

- 5.1.3. **Contrast.** Imaging contrast will not be ordered as part of this study.
- 5.1.4. **Voiding.** Participants will be asked to void their bladder immediately prior to radiotracer injection and before imaging.

5.2. **Ga PSMA-HBED-CC administration**

- 5.2.1. **Dose.** 3-7 mCi (111 – 259 MBq). Target 5 mCi.
- 5.2.2. **Route of administration.** Intravenous.
- 5.2.3. **Frequency.** Once per PET scan.
- 5.2.4. **Uptake time.** 75 minutes ± 25 minutes. Target 75 minutes

5.3. **Prohibited Medications**

None.

5.4. **PET/CT Imaging Procedures**

- 5.4.1. **Scan coverage.** Scan coverage will extend from mid-thigh to the base of the skull, starting from the mid-thighs to prevent urinary bladder radiotracer accumulation at the start of PET imaging. Subject to void immediately prior to imaging.
- 5.4.2. **Bed position.** Scan time will be dependent on scanner capabilities. At a minimum, 3 minutes per bed position will be used.
- 5.4.3. **Discharge.** Subject must be monitored for adverse events for a minimum of 2 hours post-injection.
- 5.4.4. **Local Analysis.** A board-certified nuclear medicine physician on-site will interpret the images within 3 business days of the imaging study. These interpretations will not be used for final evaluation, however regional positivity results will be collected as study data.
- 5.4.5. **Internal Blinded Reads.** Imaging data will be interpreted by two different readers in a random order at separate reading sessions. Cross sectional imaging from the PET will be available for anatomic correlation. Final reads for each subject will be interpreted as positive or negative for the presence of pelvic nodal disease, and positive or negative for the presence of osseous metastatic disease and soft tissue metastases outside of the pelvis. All readers will have undergone Ga PSMA PET training.
- 5.4.6. **Results dissemination.** Results will be shared with the subject's urologist and will be included in the subject's medical record.

5.5. **Visual Interpretation of PET data (Internal blinded reads)**

Regions of suspected disease will be graded on a two-point scale by each reader (0=Negative or 1=Positive). A region will be judged as positive if at least one lesion in this region is visually positive. Regions are defined in Table 12.1. in Section 12. Criteria for visual interpretation positive for disease are detailed in Section 12. 1.1.

- 5.5.1. **Lymph nodes.** Considered positive if Ga PSMA-HBED-CC uptake is focal and greater than adjacent background. Pelvic lymph nodes will be subclassified according to their localization as follows: R/L obturator, R/L

external iliac, R/L internal iliac, and other pelvic nodes (total of 7 subgroups).

- 5.5.2. **Visceral lesions.** Considered positive if the  $^{68}\text{Ga}$  PSMA-HBED-CC uptake is focal and greater than physiologic background activity of the involvement organ or anatomic site.
- 5.5.3. **Bone lesions.** Considered positive if the  $^{68}\text{Ga}$  PSMA-HBED-CC uptake is focal and greater than physiologic bone marrow.

## 5.6. **Post-Imaging Prostatectomy**

Prostatectomy and pelvic nodal dissection will be performed at the discretion of referring physician after reviewing imaging results. Nodal dissection should follow standard of care.

- 5.6.1. **Negative imaging.** Subjects without evidence of positive nodal or metastatic disease on  $^{68}\text{Ga}$  PSMA-HBED-CC PET imaging will undergo radical prostatectomy and pelvic nodal dissection. The pelvic nodal dissection will be performed regardless of imaging results.
- 5.6.2. **Positive imaging.** The urologist will be informed of the location of any  $^{68}\text{Ga}$  PSMA-HBED-CC PET positive (or suspicious) regional pelvic nodes prior to surgery. The surgeon should attempt to capture the suspicious node during the nodal dissection.
- 5.6.3. **Nodal dissection.** Nodes will be marked by location using the standard procedures. For example, if the urologist removed left and right nodal regions separately, the subject will have two nodal regions (left/right). If the nodes are removed in six groups (bilateral internal/external/obturator nodes), the subject will have six nodal regions analyzed.
- 5.6.4. **Pathology:** Specimens from prostatectomy will be evaluated for the presence of nodal metastasis. This will be reported on a per patient basis, and by region as positive or negative. The pathology report should list the number of nodes counted during the exam.
- 5.6.5. **Immunohistochemical staining (IHC) (optional).** Although not routinely performed during standard practice, IHC staining for PSMA of tumor specimens (primary and lymph node metastases) is preferred.

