12.2.1.3. Bone lesions: Given the high rate of false negative biopsies for osseous metastases in subjects with prostate cancer, subjects with negative bone biopsies of  $^{68}\text{Ga}$ -PSMA-HBED-CC PET positive lesions will be further evaluated:

- If pathology demonstrates an alternative diagnoses that is known to be  $^{68}\text{Ga}$ -PSMA-HBED-CC positive (eg Renal Cell Carcinoma metastases, Paget's disease), then this will be considered negative for disease.
- If pathology is indeterminate, then follow-up imaging as described below will be performed as per clinical standards at the site.

12.2.1.4. Although not routinely performed during standard practice, immunohistochemical staining for PSMA of tumor specimens (primary and lymph node metastases) may be performed, although not required.

12.2.1.5. All regions not sampled for biopsy/histopathology will be designated as indeterminate for disease by pathology. Conventional imaging follow-up may be used in these cases to determine tissue status.

12.2.2. Follow-up Imaging will be used as a secondary assessment for prostate cancer in the event pathology information is not available:

All subjects will be tracked for follow-up conventional imaging between 3-12 months post  $^{68}\text{Ga}$ -PSMA-HBED-CC (dedicated CT, MRI and/or bone scan) as per site standard of care. If no follow-up imaging has been performed within the 9 months following the  $^{68}\text{Ga}$ -PSMA-HBED-CC scan, then the research study will pay for an additional follow-up CT scan to be performed in the 9-12

month window post-Ga-PSMA-HBED-CC scan. Follow up imaging will only be performed on subjects that have positive Ga-PSMA-HBED-CC findings because conventional imaging assessment for disease is primarily targeting suspicious lesions identified by Ga-PSMA-HBED-CC PET/CT. Interpretation of follow-up imaging will be performed by local read. Preferably, the follow-up conventional imaging should be the same modality/modalities as the initial staging work-up to allow for reproducible and accurate comparisons. Conventional imaging standards as described below will be used to determine tissue positive for prostate cancer disease. Conventional imaging will not be used to determine negative prostate cancer disease regions due to its inherently low negative predictive value.

Tissue positive for prostate cancer disease based on follow-up imaging:

12.2.2.1. Lymph nodes will be assessed by change in size.

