#### 13.2.1. True positive patient:

13.2.1.1. **Ga PSMA-HBED-CC PET/CT positive for a regional node by internal blind reader:** pathology at prostatectomy is positive for a regional node that correlates in location to the PET images (location on pathology is determined by the urologist at the time of the surgery). Only one node needs to correspond between imaging and pathology for a patient to be considered a true positive.

13.2.1.2. **Ga PSMA-HBED-CC PET/CT positive for regional nodes by internal blind reader,** pathology negative for regional nodes, imaging after prostatectomy demonstrates the same node was not removed at surgery, and follow-up biopsy or imaging demonstrates presence of nodal disease as defined in Section 12.2.1.2 .

13.2.1.3. **Conventional imaging criteria for positive node on follow-up imaging:** imaging within 3-12 months, the node decreases by more than 30% (for patients undergoing systemic treatment or focal therapy at this site) or increase by more than 20% in short axis diameter in the absence of treatment (with a minimum of 3 mm in change in size) as defined in Section 12.2.2.1 .

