#### 13.2.3. False positive patient:

13.2.3.1. **Ga PSMA-HBED-CC PET/CT positive for regional nodes**

**by internal blind reader**, pathology at prostatectomy is negative, and imaging after prostatectomy demonstrates that node is no longer present as defined in Section 12.2.1.2.

13.2.3.2.  **$^{68}\text{Ga}$  PSMA-HBED-CC PET/CT positive for regional node by internal blind reader**, but pathology at prostatectomy is positive for node but in a different nodal region than the node seen on PSMA PET.

13.2.4. False negative patient:

13.2.4.1.  **$^{68}\text{Ga}$  PSMA-HBED-CC PET/CT negative for regional nodes by internal blind reader**, but pathology at prostatectomy is positive for regional nodes.

13.2.5. Non-evaluable patient:

13.2.5.1. Any subject that does not have sufficient data to meet the criteria for definition of true positive patient, true negative patient, false positive patient, or false negative will be classified as non-evaluable.

13.2.5.2. Patients with extrapelvic nodal metastases will not be included in this analysis for the primary endpoint if patients do not undergo prostatectomy.

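### Whether a man gets the pathology reference standard can depend on his PET result, and the primary analysis removes unverified men without any analysis that would show the resulting bias

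*Combined protocol and SAP*

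**What the plan says.** **Surgery and the scan.** The lead sentence of 5.6 reads "Prostatectomy and pelvic nodal dissection will be performed at the discretion of referring physician after reviewing imaging results". Under 5.4.6, "Results will be shared with the subject's urologist and will be included in the subject's medical record". For men whose scan shows neither nodal nor distant disease, 5.6.1 says that those with such "PET imaging will undergo radical prostatectomy and pelvic nodal dissection". Section 5.6.2, on positive scans, makes no matching commitment. Section 5.6.1 also says "The pelvic nodal dissection will be performed regardless of imaging results", which does not sit with the lead sentence.

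**Men without surgery.** 13.2.5.2 expects some: "Patients with extrapelvic nodal metastases will not be included in this analysis for the primary endpoint if patients do not undergo prostatectomy". For everyone else, 13.2.5.1 is the catch-all: a man whose data do not fit true positive, true negative, "false positive patient, or false negative will be classified as non-evaluable".

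**Classification without surgery.** 13.2.1.3, with 12.2.2.1, gives size-change criteria on follow-up imaging at 3 to 12 months under the true-positive heading. The true-negative, false-positive and false-negative definitions (13.2.2 to 13.2.4) all require pathology at prostatectomy. Section 12.2.2 closes the other route to a negative: "Conventional imaging will not be used to determine negative prostate cancer disease regions due to its inherently low negative predictive value". It also limits follow-up imaging to men with positive PET findings.

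**Analysis and use.** 13.2 gives descriptive summaries only. 13.1 says that the results will help set the target sensitivity for a larger study.

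**The concern.** When the chance of receiving the reference standard depends on the index test, sensitivity and specificity among verified men differ in general from those among all men scanned. Here the test result reaches the person deciding on surgery, surgery supplies the main reference standard, and men without it can leave the analysis. If PET-positive men are verified less often than PET-negative men, true positives are lost from the sensitivity calculation while false negatives stay in.

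The stake is the one purpose 13.1 gives the pilot: a sensitivity on which to size the next study. Section 13.1 also foresees combining the results with those of other sites that use the same methods. Pooling shrinks random error but leaves a shared bias untouched.

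**Working it through.** **The plan's own figure.** 13.1 gives 95% half-widths of 16.4, 15.5, 14.3, 12.8 and 10.7 points for sensitivities of 70, 75, 80, 85 and 90%. The formula 1.96 × √(p(1−p)/30) gives 16.40, 15.49, 14.31, 12.78 and 10.74, so all five reproduce. They describe random error with 30 patients and make no allowance for unverified men.

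**Inputs.** Section 2.3 reports, for the cited prospective study of 30 men, sensitivity 64%, specificity 95%, PPV 88% and NPV 82%. The cells are not printed. An exhaustive search finds one table that fits: TP 7, FN 4, FP 1, TN 18 (7/11 = 63.6%, 18/19 = 94.7%, 7/8 = 87.5%, 18/22 = 81.8%). The share f of PET-positive men not operated on is not in the documents. It is an assumption, shown up to 50%.

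**Case 1: only PET-positive men lost, none recovered by imaging.**
- Observed sensitivity = Se(1−f) / [Se(1−f) + (1−Se)]
- Observed specificity = Sp / [Sp + (1−Sp)(1−f)]

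| f | Sensitivity | Specificity |
|---|---|---|
| 0 | 7/11 = 63.6% | 18/19 = 94.7% |
| 25% | 5.25/9.25 = 56.8% | 18/18.75 = 96.0% |
| 30% | 4.9/8.9 = 55.1% | 18/18.7 = 96.3% |
| 50% | 3.5/7.5 = 46.7% | 18/18.5 = 97.3% |

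At a true sensitivity of 80% (13.1 anticipates more than that), f = 30% gives 0.56/0.76 = 73.7% and f = 50% gives 0.40/0.60 = 66.7%.

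**Case 2: follow-up imaging recovers true positives (f = 30%).**
- Half recovered: TP = 4.9 + 1.05 = 5.95. Sensitivity is 5.95/9.95 = 59.8% and PPV is 5.95/6.65 = 89.5%.
- All recovered: TP = 7. Sensitivity is 7/11 = 63.6%, so that bias is gone, and PPV is 7/7.7 = 90.9%.
- Specificity stays at 96.3% in both, because no unoperated man can be classed as a false positive.

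**Case 3: only node-positive PET-positive men go unoperated (f = 30%, none recovered).** Sensitivity is again 55.1%, specificity is unchanged at 94.7%, and PPV falls to 4.9/5.9 = 83.1%.

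**Case 4: men negative in the pelvis but positive elsewhere are lost.** They are PET-negative for the primary endpoint, yet 5.6.1 does not commit them to surgery, and 13.2.5.2 removes those with extrapelvic nodal metastases who are not operated on. Losing one false negative gives 7/10 = 70.0%. Losing one true positive and one false negative gives 6/9 = 66.7%. Both exceed 63.6%.

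**Bounds, whole-patient example.** Suppose two true positives and one false negative are unverified. The verified cells are TP 5, FN 3, FP 1, TN 18, and complete-case sensitivity is 5/8 = 62.5%.
- PET-positive men counted as node-positive and the PET-negative man as node-negative: sensitivity 7/10 = 70.0%, specificity 19/20 = 95.0%.
- The reverse: sensitivity 5/9 = 55.6%, specificity 18/21 = 85.7%.
- All three node-positive gives sensitivity 7/11 = 63.6%, and all three node-negative gives 5/8 = 62.5%.

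The two PET groups must therefore be set separately to reach the extremes.

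**The case against.** **Unoperated men are not all discarded.** A reader might infer that they are. The documents support that only for unoperated men with extrapelvic nodal metastases. Section 13.1 accepts pathology, follow-up imaging or both, and 12.2.2 provides for a study-paid CT at 9 to 12 months where no earlier follow-up imaging exists. This stands, and Case 2 shows that it can remove the loss of sensitivity. But the route leads only to true positive. Nor does 13.2.1.3 say whether it covers men without surgery or only supplies the imaging criterion for 13.2.1.2, which concerns operated men.

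**The 5.6.1 sentence on dissection promises full verification.** It conflicts with the lead sentence of 5.6 and with 13.2.5.2, which plans for unoperated men. It cannot be relied on until the three are reconciled.

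**The target is sensitivity against prostatectomy pathology (1.1.1), so operated men are the right group.** That is a defensible target, but the group would be selected partly on the test under study, and the plan does not say so.

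**The shift is within sampling error in a descriptive pilot.** At f = 25% the fall is 6.8 points, against planned half-widths of 14 to 16 points at 70 to 80%. That is true and lowers the stakes. It does not remove a bias that would pass into the next design.

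**Begg-Greenes would settle it.** It returns 63.6% and 94.7% in Case 1 only because that example removes true and false positives at the same rate, which is the method's own assumption. The one exclusion that the plan names depends on disease extent. In addition, the surgeon sees the local read, while the endpoint uses the blinded read (5.4.4, 12.1).

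**Conclusion.** The point holds as a risk of verification bias that the planned analysis could not detect. Its direction and size are conditional.

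A reader might infer that sensitivity must be biased down and specificity up. The documents do not support that without conditions: specificity moves only if some unverified PET-positive men are node-negative, and Case 4 reverses the direction for sensitivity. Nor can PPV be treated as unaffected; in the f = 30% examples it runs from 83.1% to 90.9% against a true 87.5%. If verification fails equally in PET-positive and PET-negative men, regardless of disease status, there is no bias.

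Under the reconstructed cells, with only PET-positive men lost and none recovered, sensitivity falls by 6.8 points at f = 25% and by 16.9 points at f = 50%. Specificity rises by at most 2.6 points over that range. The values of f and the recovery rates are assumptions.

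**What to change.** Add to 13.2:

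1. A table of all scanned men by blinded pelvic result, local result, extrapelvic result and verification route (surgery, follow-up imaging, none).
2. Alongside the complete-case result, best and worst bounds for sensitivity and specificity that cover all unverified men. Count unverified PET-positive men as node-positive and then as node-negative, and unverified PET-negative men likewise, setting the two groups separately.
3. A Begg-Greenes estimate as a secondary analysis only, stating that it assumes verification depends solely on the PET result or results conditioned on.
4. A statement of whether 13.2.1.3 applies to unoperated men, with results shown with and without them.

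Reconcile the discretion sentence in 5.6, the dissection sentence in 5.6.1, and 13.2.5.2. No position is taken here on the surgical rule.

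The additions use data that the study already plans to collect, need no significance testing and change no care. The drawback is that the bounds will be wide if many men are unverified.

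### Pelvic nodes are verified more fully when PET flags them than when it does not, which pushes per-patient sensitivity and NPV upward by an amount the documents do not fix

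*Combined protocol and SAP*

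**What the plan says.** Section 5.6 leaves prostatectomy and dissection "at the discretion of referring physician after reviewing imaging results" and says of the technique only that "Nodal dissection should follow standard of care". For negative scans, 5.6.1 adds: "The pelvic nodal dissection will be performed regardless of imaging results". For positive scans, 5.6.2 has the urologist told the location of "PET positive (or suspicious) regional pelvic nodes prior to surgery", and continues: "The surgeon should attempt to capture the suspicious node during the nodal dissection".

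No common template is set. On specimen handling, 5.6.3 says: "Nodes will be marked by location using the standard procedures". Its examples are a two-region (left/right) and a six-region dissection. PET is read in seven pelvic subgroups, the seventh being other pelvic nodes (5.5.1, Table 12-2).

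The per-patient rules for the primary endpoint are these:

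- **True positive.** Pathology matches the PET location (13.2.1.1). Alternatively, surgery missed the flagged node and later biopsy or imaging shows nodal disease (13.2.1.2, 13.2.1.3).
- **True negative.** The blinded read and the prostatectomy pathology are both negative; no follow-up is required (13.2.2.1).
- **False negative.** The blinded read is negative and prostatectomy pathology is positive (13.2.4.1). No other route is given.

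Section 12.2.2 confines follow-up imaging performed for the study to men with positive PET findings.

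**The concern.** The reference standard should find nodal disease equally well whatever the scan showed. Here the search is partly steered by the scan. Consider a man whose only nodal disease lies outside the tissue his surgeon would normally remove. If PET flags it, the surgeon is asked to go after it, and if surgery misses it, later biopsy or imaging can still confirm it. If PET misses it, nothing sends the surgeon there, negative pathology makes him a true negative, and later evidence cannot reclassify him.

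True positives are thus gained, and false negatives lost, in the same group of men. Sensitivity and NPV both move upward. Section 13.1 intends the pilot's results, possibly combined with those of other sites using the same methods, to set the sensitivity that powers a larger study. Pooling shrinks random error but not a bias that all the sites share.

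**Working it through.** **The plan's own figures.** Section 13.1 tabulates 95% half-widths for 30 patients. With 1.96 × √(p(1−p)/30), p = 70, 75, 80, 85 and 90% give 16.40, 15.49, 14.31, 12.78 and 10.74 points. The table (16.4, 15.5, 14.3, 12.8, 10.7) reproduces. It takes all 30 men as the denominator. Section 13.1 also prints TP/(TP+FP) as sensitivity, which is positive predictive value; sensitivity below means TP/(TP+FN).

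**Inputs from the documents**

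- True sensitivity s: 65%, the middle of the 64–66% cited in Section 2.4, and 80%, the lower edge of what Section 13.1 anticipates.
- Node-positive prevalence, derived from Section 2.3. The 130-patient retrospective study reports sensitivity 65.9%, specificity 98.9% and accuracy 88.5%, which imply (0.989 − 0.885)/(0.989 − 0.659) = 0.315, or 41 of 130. The 30-man prospective study fits 11 node-positive men: 7/11 = 64%, 18/19 = 95%, 7/8 = 88%, 18/22 = 82%. Among 30 men this means about 9 to 11 node-positive.

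**Assumptions, since the documents give no value**

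- f: share of node-positive men whose only pelvic nodal disease lies outside the usual dissection; shown for 5% to 30%.
- c: share of PET-flagged outside disease captured at surgery or confirmed later; shown at 1 and 0.5.
- PET is equally sensitive inside and outside the usual dissection; the on-site and blinded reads agree; flagged outside disease that is neither captured nor confirmed drops out as non-evaluable (13.2.5.1).

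**Formula.** Per node-positive man:

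- TP = s(1−f) + s·f·c
- FN = (1−s)(1−f)
- apparent sensitivity = TP/(TP+FN)

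Example with s = 0.65, f = 0.20, c = 1: TP = 0.65, FN = 0.35 × 0.80 = 0.28, and 0.65/0.93 = 69.9%.

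| f | s=65%, c=1 | s=65%, c=0.5 | s=80%, c=1 | s=80%, c=0.5 |
|---|---|---|---|---|
| 5% | 66.2 | 65.6 | 80.8 | 80.4 |
| 10% | 67.4 | 66.2 | 81.6 | 80.9 |
| 20% | 69.9 | 67.6 | 83.3 | 81.8 |
| 30% | 72.6 | 69.3 | 85.1 | 82.9 |

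The bias vanishes only if f = 0 or c = 0.

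**In men.** The number of false negatives booked as true negatives is D(1−s)f, where D is the number of node-positive men. It runs from 9.45 × 0.20 × 0.05 = 0.1 to 11 × 0.35 × 0.30 = 1.2.

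**NPV.** Take s = 65%, f = 20%, prevalence 31.5% and an assumed specificity of 97% (the two studies report 95% and 98.9%). True negatives are 30 × 0.685 × 0.97 = 19.93 and false negatives 9.45 × 0.35 = 3.31. The true NPV is 19.93/23.24 = 85.8%. Moving 3.31 × 0.20 = 0.66 men across gives 20.59/23.24 = 88.6%.

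**Against sampling error.** With 9 to 11 node-positive men, the same half-width formula gives 31.2 to 28.2 points at s = 65% and 26.1 to 23.6 at s = 80%.

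**Restricted analysis.** If the PET call and the reference are both limited to standard sites, TP = s(1−f) and FN = (1−s)(1−f). The ratio is s for any f and c, where s is now the sensitivity at those sites.

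**The case against.** Section 5.6 prescribes standard-of-care dissection for everyone, and 5.6.2 asks for the flagged regional node to be captured within that dissection. It does not say the field is widened. If flagged nodes simply fall inside the usual specimen, f is near zero. The mismatch between six dissection groups and seven PET subgroups is weak evidence, because the six are offered only as an example. This stands as a limit on size. It does not equalise verification: doing a dissection in every man says nothing about its targeting, and the follow-up route to a true positive is still open only after a positive scan.

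A reader might infer that disease missed by PET can never be counted. The documents do not support that. The surgeon acts on the on-site result, including findings that are merely suspicious, while the endpoint uses the blinded reads (5.4.4 to 5.4.6). A man flagged on-site but negative on the blinded read can have a directed dissection and become a false negative.

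A reader might also infer that the recorded data cannot reveal the bias at all. In fact on-site regional results, pathology by region and node counts are collected (5.4.4, 5.6.4). They help where nodes are labelled in six groups. They help little where labels are only left and right, or where extra tissue lies within a named region.

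The rule "Only one node needs to correspond between imaging and pathology for a patient to be considered a true positive" is not part of this mechanism. Targeting also has a benefit: Section 12.2.1 aims for histological confirmation of positive findings, and without it more PET-positive men would depend on follow-up imaging or be non-evaluable.

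**Conclusion.** The point holds as a partial dependence of the reference standard on the scan, upward in direction for sensitivity and NPV. For f of 5% to 30%, the bias at s = 65% is about +1 to +8 points with complete capture and +0.6 to +4 with half capture. At s = 80% it is about +1 to +5 and +0.4 to +3. These are scenarios, not estimates: the documents support no particular f or c, and full capture is the upper end because 5.6.2 asks only for an attempt and both rescanning and biopsy are optional (5.7.1, 5.7.3).

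In a descriptive pilot of 30 men the effect amounts to about one man at most and is well below sampling error, so it does not invalidate the study. It deserves action because it is systematic, feeds the sizing of the next trial, and is cheap to expose.

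**What to change.** Leave surgery as it is.

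1. **Section 5.6.3.** Have the surgeon record the intended standard dissection sites before the PET result is released, and mark each packet as inside that list or added because of PET. The timing matters: asked afterwards, whether tissue would have been removed anyway is an unblinded judgement. Planned dissection is already an eligibility criterion (3.1.4), so the list can be taken at enrolment.
2. **Section 13.2.** Pre-specify a second per-patient table in which the blinded PET call and the reference are both limited to the listed sites and to prostatectomy pathology, without the follow-up route of 13.2.1.2 and 13.2.1.3. Report it beside the full table as now defined.
3. **Node counts.** Tabulate the counts from 5.6.4 by PET result.
4. **Limitation.** State that more diligent sampling within standard sites after a positive scan is not corrected.

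The cost is the site list and packet mark on the form, and one extra table. The restricted sensitivity may be slightly lower, rests on fewer events, and does not speak to disease outside the standard sites. Because that table relies on pathology alone, a flagged node left behind at a listed site counts against PET, so its specificity and PPV may be conservative. That is why both tables are needed.
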